6. PRIOR AND CONCOMITANT THERAPY

All therapies other than the study drug administered from signing of informed consent until the last study visit must be recorded in the electronic data capture (EDC) system (name of the drug and dates of administration). Intake of concomitant medication(s) will be monitored continuously from signing of Informed Consent Form (ICF) until the last study visit.

6.1 PRIOR MEDICATIONS

All medications the subject has taken within 14 days of study drug administration will be documented in the EDC. Influenza vaccination within the prior 6 months will also be documented in the EDC. The use of over the counter, symptom-modifying drugs such as NSAIDS, antihistamines, or pseudoephedrine are prohibited in the 6 hours prior to dosing of study drug with the exception of the pretreatment medications.

6.2 PERMITTED CONCOMITANT THERAPIES

The use of contraception and acetaminophen (paracetamol), as per license, is allowed during the study. As the impact of VIS410 on symptoms of influenza is a secondary objective of this study, the use of acetaminophen (paracetamol) should be minimized.

Chronic medications not listed in excluded concomitant medications, are permitted where the dose has been stable for at least 3 months prior to screening.

The use of symptom-modifying drugs such as NSAIDS, antihistamines, or pseudoephedrine are discouraged and in case a symptom modifying agent is needed, paracetamol/acetaminophen should be encouraged as the drug of choice.

In case of clinical worsening of influenza-related symptoms recorded at baseline or development of two new influenza-related symptoms 48 hours after study drug administration, additional antiviral prescription medication may be used, at the discretion of the Investigator, for management of influenza-like symptoms per standard of care. Investigator can decide to initiate antiviral therapy sooner as needed for subject safety and well-being.

6.3 EXCLUDED CONCOMITANT MEDICATIONS

Consistent with exclusion criteria, the use of antivirals should be excluded except as outlined in Section 6.2. Excluded antiviral medications include, but are not limited to: rimantadine, amantadine, peramivir, zanamivir, laninamivir or oseltamivir.

Use of antibiotics is discouraged unless there is a documented or suspected bacterial infection.

7. ASSESSMENTS

AEs and concomitant medications will be recorded from signing of the ICF to the subject's last visit.

7.1 TIMING OF ASSESSMENTS

If the following assessments are planned at the same time, the order of assessments should be as follows:

- 1) Influenza Patient Reported Outcomes questionnaire
- 2) Vital signs
- 3) Nasopharyngeal swab
- 4) Blood sampling

7.1.1 *Screening Examination and Eligibility Screening Form*

All subjects must provide written informed consent before any study specific assessments or procedures are performed.

Subjects will be assigned a unique screening number prior to Rapid Antigen Testing. Following confirmation of influenza A infection, subjects will be assessed for inclusion and exclusion criteria and those who fulfill all the inclusion and none of the exclusion criteria will be randomized into the study.

A screen failure log must be maintained by the Investigator for all entry criteria failures.

7.1.2 *Contraception Requirements*

All women of childbearing potential and all male subjects must practice effective contraception from screening until 60 days post-infusion. For the purposes of this study, women who do not meet one of the following criteria listed below are considered to be physiologically capable of becoming pregnant and are, therefore, defined as women of childbearing potential:

- Non-childbearing potential:
 - Post-menopausal: ≥ 12 months of natural (spontaneous) amenorrhea or
 - 6 weeks after surgical bilateral oophorectomy with or without hysterectomy or
 - follicle stimulating hormone > 40 mIU/mL
 - hysterectomy
 - bilateral tubal ligation

Women of childbearing potential and all male subjects participating in heterosexual sexual relations must be willing to practice effective contraception from screening until 60 days post-infusion. For the purposes of the study, highly effective contraception is defined as:

- Combination of an established form of hormonal contraception (oral, injected, or implanted) or an intrauterine device or intrauterine system

and

- A physical barrier method of contraception with use of a spermicide such as condom or occlusive cap (diaphragm or cervical/vault caps) with spermicidal foam/gel/film/cream suppository. The use of barrier contraceptives should always be supplemented with the use of a spermicide, unless not available in a country
- Male vasectomy with negative semen analysis documentation. The use of contraception does not apply if the male partner has been vasectomized at least 6 months prior to dosing
- Complete abstinence can be considered an acceptable method of contraception at the discretion of the Investigator. Periodic abstinence (e.g., calendar, ovulation, symptothermal, or post-ovulation methods) and withdrawal are not considered acceptable methods of contraception

The combination of 2 barrier methods, periodic abstinence (e.g., calendar, ovulation, symptothermal, or post-ovulation methods), and withdrawal are not considered acceptable methods of contraception.

Pregnancy reporting is described in Section 10.8.

7.1.3 *Procedures for Enrollment of Eligible Subjects*

Once a subject has fulfilled the entry criteria, he/she will be assigned a unique identifier. The site will randomize the subject using the Interactive Web Response System (IWRS).

7.1.4 *Clinical Assessments and Procedures*

When required, subjects may be given a pre-screening informed consent in order to perform the Rapid Antigen Test for influenza. Flu-positive subjects will then be given a full explanation of the nature of the study and written informed consent (approved by the local ethics committee) will be obtained according to local requirements before any study-related assessment will be carried out.

At screening, subjects will be requested to attend the clinical center to have assessments performed as described in the Time and Events Schedule.

All results from the screening procedures required to evaluate eligibility must be available prior to drug infusion on Day 1. Any abnormal assessment at the screening visit will be assessed according to its clinical relevance, and if found relevant, the subject will not be included in the study.

On Day 1, eligibility of the subjects will be confirmed and assessments will be performed as described in the Time and Events Schedule.

Subjects will be admitted to the clinical center on Day 1 and will remain at the clinical center until at least 2 hours after study drug infusion on Day 1 and discharged if considered safe by the investigator. Prior to discharge, all subjects will be counseled on the potential GI AEs and management of these events. Subjects will have a follow-up phone call in the evening of the dosing day to ensure safety and well-being.

Follow-up Clinic Visits and Telephone Calls:

All subjects will be asked to come back to the clinical center for follow-up visits on Day 3 (± 1 day), 5 (± 1 day), 7 (± 1 day), 14 (± 3 days), 28 (± 3 days), 56 (± 7 days), and Day 100 (± 7 days). In order to provide some flexibility for the subjects regarding the site visits and to maintain the integrity of the study design, a time window is permitted for the follow-up visits in case of time conflict or unforeseen circumstances.

In addition, between clinic visits up to Day 7 (e.g., Days 2, 4 and 6) subjects will receive a follow-up telephone call to ensure compliance with FluPRO Influenza Symptom Questionnaire and review any new or worsening signs or symptoms.

Subjects who terminate the study before completion of the scheduled study procedures for any reason (AE, withdrawal of consent, etc.) should be asked to complete study assessments (including safety) prior to withdrawal if possible. Subjects who withdraw for safety reasons should come for a safety follow-up visit as soon as possible within 14 days after discontinuation.

7.1.5 Virological Assessments

The virological laboratory assessments are:

- At screening, a single nasopharyngeal swab will be obtained from one nostril for the rapid test.
- A nasopharyngeal swab will be collected from each nostril as described in the schedule of assessments and laboratory manual. These swabs will be sent to a central virology laboratory for processing into appropriate aliquots for virology and analysis as detailed in Sections 7.2.1, 7.3.1, 7.4, and 7.5.
- Further details on sample collection, processing, shipment, and storage will be described in the laboratory manual.
- Virology samples taken from all subjects may be infectious and will be classified as “diagnostic specimens” for dispatch purposes.
- The Investigator may also perform additional tests in the local laboratory consistent with standard of care for the illness being treated.

7.1.6 Unscheduled Visits

Unscheduled visits can be planned at the discretion of the Investigator to obtain additional information to ensure the safety of the subject.

Subjects will be instructed to contact the trial center if they exhibit worsening symptoms or new episode of influenza-like illness so that they may be monitored and asked to return to the site for additional assessments (safety, nasopharyngeal swabbing) at the Investigator’s discretion. Findings made during unscheduled visits should be reported in the EDC system and should be reported in the source documents.

7.2 PHARMACOKINETIC EVALUATIONS

7.2.1 *Sample Collection and Handling*

Throughout the study, 5 mL venous blood samples will be collected for analysis of VIS410 in serum, according to the time points defined in the Time and Events Schedule. The exact date and time of blood sampling and of administration of the study drug must be recorded in the EDC system.

Blood samples will be collected by venipuncture or via indwelling cannula in the forearm into standard serum separator tubes and will be immediately chilled (ice bath). Further procedures for sample collection, shipment, processing, and storage will be described in the laboratory manual.

Nasopharyngeal swabs for determination of VIS410 concentration from nasopharyngeal secretions will be taken at the time points defined in the Time and Events Schedule. Further details on sample collection, processing, shipment, and storage will be described in the laboratory manual.

7.2.2 *Bioanalysis*

Serum samples and nasopharyngeal swabs for determination of the concentration of VIS410 will be analyzed under the responsibility of the Sponsor.

7.2.3 *Pharmacokinetic Parameters*

Standard non-compartmental approaches using Phoenix WinNonlin (Pharsight Corporation, Princeton, NJ, USA; Version 6.3 or higher) will be used to estimate PK parameters in serum and from nasopharyngeal secretions as described below.

The following PK parameters will be determined for VIS410 in serum and/or from nasopharyngeal secretions:

- C_{\max} : maximum observed concentration
- T_{\max} : time of C_{\max}
- $AUC_{0-\infty}$: area under the concentration-time curve from time 0 extrapolated to infinity
- $AUC_{0-\text{last}}$: area under the concentration-time curve from time 0 to the last measurable concentration
- $t_{1/2}$: terminal elimination half-life
- CL: total clearance (serum only)
- V_d : volume of distribution (serum only)
- Ratio of nasal:serum AUC

Additional PK parameters may be determined as appropriate. PK data from this study will be also analyzed by population PK modeling as appropriate.

7.3 ILLNESS EVALUATIONS

7.3.1 *Viral Shedding*

Nasopharyngeal swabs to determine viral shedding will be taken as indicated in the Time and Events Schedule. Further details on sample collection, processing, shipment, and storage will be described in the laboratory manual.

7.3.2 *Signs and Symptoms of Influenza*

The FluPRO questionnaire will be completed by the subject at the time points indicated in the Time and Events Schedule.

Unsolicited (i.e., not collected via the FluPRO questionnaire) signs and symptoms will be collected and scored via a targeted physical exam that will be performed by the Investigator or designee. Timing of this assessment is provided in the Time and Events Schedule and is to be performed at the discretion of the Investigator or designee.

Body temperature will also be measured. Fever is defined as a body temperature $\geq 38^{\circ}\text{C}$.

The solicited and unsolicited signs and symptoms of influenza will not be reported as AEs as these constitute an endpoint of the study and will be recorded as such, unless a situation arises whereby it is the opinion of the Investigator to do so.

7.4 IMMUNOLOGY

Blood samples for immunology assessments will be collected at the time points indicated in the Time and Events Schedule according to the instructions provided in the laboratory manual.

7.4.1 *ADA Response*

Throughout the study, 5 mL venous blood samples will be collected to determine anti-VIS410 antibody titers according to the time points defined in the Time and Events Schedule and according to the instructions provided in the laboratory manual. The exact date and time of blood sampling must be recorded in the EDC system. Anti-VIS410 antibody titers will be determined by Visterra or designee. These samples may be stored for further characterization of the effect of ADA on neutralization in accordance with local regulations.

7.4.2 *Anti-Influenza Antibody Response*

Venous serum samples (5 mL) will be collected to determine anti-influenza antibody titers according to the time points defined in the Time and Events Schedule and according to the instructions provided in the laboratory manual. Anti-influenza antibody titers will be determined by Visterra or designee.

7.5 RESISTANCE ANALYSIS

Analysis of resistance will be performed by Visterra or designee on selected samples from nasopharyngeal swabs. Further procedures for sample collection, processing, shipment, and storage will be described in the laboratory manual.

7.6 SAFETY EVALUATIONS

The safety assessment in this study will be based on AEs, clinical laboratory tests, vital signs, and physical examination, as described in the following sections.

7.6.1 *Adverse Events*

AEs will be monitored continuously from signing of informed consent until the last study-related activity. At regular intervals during the study, subjects will be asked non-leading questions to determine the occurrence of any AEs. All AEs reported spontaneously during the course of the study will be recorded as well.

Subjects will be observed during infusion and for at least 2 hours after completion of administration of study treatment to allow monitoring for possible hypersensitivity reactions, anaphylactic reactions, or other AEs that occur during this time period.

All AEs will be recorded in the EDC system, except for the symptoms of influenza collected via the FluPRO questionnaire as discussed in Section 7.3.2.

For detailed definitions and reporting procedures of AEs, see Section 10.

7.6.2 *Clinical Laboratory Tests*

Blood samples will be collected by venipuncture or via indwelling cannula at the time points indicated in the Time and Events Schedule.

Standard laboratory tests will be performed by a central or local laboratory. Appendix 1 lists the biochemistry, hematology, coagulation, and serology tests that will be performed on the safety blood samples.

Creatine kinase-MB, creatinine kinase, and troponin are to be measured in the case where the subject has chest pain.

A midstream urine sample will be collected for urinalysis by dipstick, flow cytometry, and microscopic examination. Appendix 1 lists the urinalysis parameters that will be assessed.

Urine pregnancy tests will be performed at the time points indicated in the Time and Events Schedule.

The Investigator must review the laboratory report, document this review, and record any change occurring during the study he/she considers to be clinically relevant in the EDC system. Laboratory values outside the normal range will be flagged and their clinical relevance will be assessed by the Investigator.

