10. ADVERSE EVENT REPORTING

10.1 DEFINITIONS

Type of Event	Collection Period
AESIs ^a	28 days after drug administration
TEAEs	Entire study period ^b
SAEs ^c and Pregnancies	Entire study period ^{b, d}

^a If a subject was enrolled with a concurrent AESI, received investigational product, and then has worsening of an AESI (severity of symptoms), then this event should also be reported.

^b The entire study period is from the time a subject receives the study drug through the Day 100 Visit.

^c If the Investigator becomes aware of any related SAE after completion of the study, he or she is obligated to report this event.

^d If a subject or the female partner of a male subject, becomes pregnant during the study or within 100 days following study drug infusion, the Sponsor must be notified within 24 hours of the site's knowledge of the pregnancy; the subject or partner will be followed until the end of the pregnancy; and the infant will be followed for 1 year after the birth, provided informed consent is obtained.

Adverse Event

An AE is any untoward medical occurrence in a patient administered a medicinal (investigational or non-investigational) product in a clinical study. An AE does not necessarily have a causal relationship with the treatment. An AE can therefore be any unfavorable and unintended sign (including an abnormal finding), symptom, or disease temporally associated with the use of a medicinal (investigational or non-investigational) product, whether or not related to that medicinal (investigational or non-investigational) product.

This includes any occurrence that is new in onset or aggravated in severity or frequency from the baseline condition, or abnormal results of diagnostic procedures, including clinical laboratory test abnormalities.

New or worsening symptoms of influenza including cough, sore throat, nasal congestion, fatigue, headache, myalgia or low-grade fever should not be reported as AEs unless they result in an SAE (i.e., lead to hospitalization).

Adverse Event of Special Interest

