An AESI (serious or non-serious) is one of scientific and medical concern specific to the Sponsor's product or program, for which ongoing monitoring and rapid communication by the Investigator to the Sponsor will be warranted. Such an event might warrant further investigation in order to characterize and understand it. Depending on the nature of the event, rapid communication by the trial Sponsor to other parties (e.g., regulators) might also be warranted (based on CIOMS VI).

For VIS410, the AESIs include the following:

- Abdominal cramping
- Diarrhea
- Nausea and vomiting
- Pruritus
- Rash

- Hypotension
- Throat tightening
- Trouble breathing or wheezing

Serious Adverse Event

An SAE is any untoward medical occurrence that at any dose meets any of the following conditions:

- results in death
- is life-threatening, i.e., the patient was at risk of death at the time of the event (e.g., ventricular fibrillation and anaphylaxis). The term does not refer to an event which hypothetically might have caused death if it were more severe.
- requires inpatient hospitalization or prolongation of existing inpatient hospitalization: Hospitalization refers to an overnight admission into hospital for the purpose of investigating and/or treating the AE. Hospitalization for an elective procedure, or routinely scheduled treatment for a pre-existing condition that has not worsened, is not an SAE.
- results in persistent or significant disability/incapacity, i.e., causing substantial disruption of the patient's ability to conduct normal life
- is a congenital anomaly/birth defect
- is medically significant, i.e., may not be immediately life-threatening or result in death or hospitalization but may jeopardize the patient's health or may require intervention to prevent one of the above outcomes. Examples of such events are intensive treatment in an emergency room or at home for allergic bronchospasm, blood dyscrasias, or convulsions that do not result in hospitalization or development of drug dependency or drug abuse.

Unlisted (Unexpected) Adverse Event

An AE is considered unlisted if the nature or severity is not consistent with the applicable product reference safety information (Investigator Brochure [5]).

Suspected Unexpected Serious Adverse Reactions

Suspected unexpected serious adverse reactions (SUSARs) are SAEs that are unexpected and judged by the Investigator or Sponsor to be related to the study treatment administered.

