9.1 Main Efficacy Analysis

9.1.1 Patient Diary - Influenza Patient Reported Outcomes (FluPRO)

The FluPRO is a 32 question instrument that assesses occurrence and severity of influenza symptoms over the last 24 hours. The instrument questions, and the conversion from text to numeric values, are presented in Sec. 17.3.

The FluPRO data is collected at Day 1: Baseline, then every day through Day 10. These data will be summarized at each visit with counts and percentages by treatment group, including a combined low-dose and high-dose VIS410 group. This analysis will be performed using the mITT population.

The domain, component, and total symptom scores for an individual will be calculated as the mean of the questions that are non-missing. The minimum data requirement for calculating each of the domain symptom scores is: nose 3 of 4 items, throat 2 of 3 items, eyes 2 of 3 items, chest/respiratory 5 of 7 items, gastrointestinal 3 of 4 items, and body/systemic 8 of 11 items. Total symptom scores will only be calculated if the conditions of missing data for all domains are met.

The domain symptom scores are defined as:

- Nose: Running or dripping nose, congested or stuffy nose, sneezing, sinus pressure
- Throat: Scratchy or itchy throat, sore or painful throat, difficulty swallowing
- Eyes: Teary or watery eyes, sore or pain eyes, eyes sensitive to light
- Chest/Respiratory: Trouble breathing, chest congestion, chest tightness, dry or hacking cough, wet or loose cough, coughing, coughed up mucus or phlegm
- Gastrointestinal: Nausea, stomach ache, vomiting, diarrhea
- Body/Systemic: Felt dizzy, head congestion, headache, lack of appetite, sleeping more than usual, body aches or pains, weak or tired, chills or shivering, felt cold, felt hot, sweating

The component symptom scores are defined as:

- Upper Respiratory Tract: Runny or dripping nose, congested or stuffy nose, scratchy or itchy throat, sore or painful throat, sneezing, difficulty swallowing, teary or watery eyes, sore or painful eyes, eyes sensitive to light,
- Lower Respiratory Tract: Trouble breathing, chest congestion, chest tightness, coughing, dry or hacking cough, wet or loose cough, coughed up mucus or phlegm
- Generalized: Nausea, vomiting, diarrhea, stomach ache, felt dizzy, sinus pressure, head congestion, headache, lack of appetite, sleeping more than usual, body aches or pains, weak or tired, chills or shivering, felt cold, felt hot, sweating

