16.3 FluPRO Questionnaire

The FluPRO questionnaire collects information on influenza symptoms over the last 24 hours. These questions have possible answers of Not at all, A little bit, Somewhat, Quite a bit, or Very much. 'Not at all' is considered 'no symptom'.

1. Runny or dripping nose
2. Congested or stuffy nose
3. Sinus pressure
4. Scratchy or itchy throat
5. Sore or painful throat
6. Difficulty swallowing
7. Teary or watery eyes
8. Sore or painful eyes
9. Eyes sensitive to light
10. Trouble breathing
11. Chest congestion
12. Chest tightness
13. Dry or hacking cough
14. Wet or loose cough
15. Felt nauseous
16. Stomach ache
17. Felt dizzy
18. Head congestion
19. Headache
20. Lack of appetite
21. Sleeping more than usual
22. Body aches or pains
23. Weak or tired
24. Chills or shivering
25. Felt cold
26. Felt hot
27. Sweating

For numeric summaries, Not at all = 0; A little bit=1; Somewhat=2; Quite a bit=3; Very much=4.

These questions have possible answers of Never, Rarely, Sometimes, Often, Always. 'Never' is considered 'no symptom'.

28. Sneezing
29. Coughing
30. Coughed up mucus or phlegm

For numeric summaries, Never = 0; Rarely = 1; Sometimes =2; Often = 3; Always = 4'.

These questions have possible answers of 0 times, 1 time, 2 times, 3 times, 4 or more times. '0 times' is considered 'no symptom'.

31. How many times did you vomit?
32. How many times did you have diarrhea?

For numeric summaries 0 times = 0; 1 time = 1; 2 times = 2; 3 times = 3; 4 or more times = 4.

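### No rule says whether a GI symptom that is both a FluPRO item and an AESI is recorded as an AE, so the GI counts behind the primary endpoint and the DSMB convening rules may run low

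*Protocol*

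**What the plan says.** **Recording rule.** Protocol 7.6.1 says: "All AEs will be recorded in the EDC system, except for the symptoms of influenza collected via the FluPRO questionnaire", and refers to 7.3.2. That section says: "The solicited and unsolicited signs and symptoms of influenza will not be reported as AEs as these constitute an endpoint of the study", with one way out: "unless a situation arises whereby it is the opinion of the Investigator to do so". SAP 9.1.1 treats all 32 FluPRO items as influenza symptoms, collected at baseline and daily to Day 10. One domain is "Gastrointestinal: Nausea, stomach ache, vomiting, diarrhea"; trouble breathing sits in the chest domain.

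**AESI rule.** Protocol 10.1 opens its list with "For VIS410, the AESIs include the following". Among its eight entries are abdominal cramping, diarrhea, nausea and vomiting, and trouble breathing or wheezing. The collection period is 28 days. Footnote a covers a subject enrolled with a concurrent AESI who is dosed and "then has worsening of an AESI (severity of symptoms), then this event should also be reported".

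**Exceptions.** Three sections give three different grounds for reporting an influenza symptom as an AE: Investigator opinion (7.3.2), a relationship to study medication (9.3.8), and resulting in an SAE (10.1).

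**Use of the data.** AESIs are part of the primary endpoint (Protocol 3.1). SAP 12.1 identifies them only from the event-type field of the eCRF. Under Protocol 5.6 the DSMB convenes, after its first meeting, if the overall GI adverse event rate reaches 50% or the moderate GI adverse event rate reaches 25%. The dosing pause in 8.3 is worded differently: it counts Grade 3 GI symptoms in 25% or more of subjects.

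**The concern.** GI events are the main known toxicity of VIS410 (Protocol 1.3 and 1.5). They are also plausible complaints in a patient with influenza, and the diary asks about them every day. A blinded site therefore has a textual basis for treating post-infusion nausea or diarrhea as a FluPRO endpoint and leaving it out of the AE record, and another for reporting it as an AESI. With roughly 50 to 75 sites, practice could differ.

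At stake are the AESI proportions in the primary endpoint and the GI rates that decide whether the DSMB is convened outside its scheduled reviews. Both come from recorded AEs, so an event held only in FluPRO counts toward neither.

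**Working it through.** The plan states no figure to reproduce here, so the check is mainly a side-by-side reading, followed by an illustration.

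**1. Overlap (Protocol 10.1 against SAP 16.3).**

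| AESI | FluPRO item |
|---|---|
| Abdominal cramping | 16, stomach ache (nearest item, not the same term) |
| Diarrhea | 32 |
| Nausea and vomiting | 15 and 31 |
| Trouble breathing or wheezing | 10, trouble breathing |
| Pruritus, rash, hypotension, throat tightening | none |

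Four of the eight AESIs overlap, including all three GI entries.

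**2. Timing.** In VIS-C001 the loose stools began about 2 to 4 hours after dosing. In the pretreated groups of VIS410-102, GI events are described as late as about 22 hours after the start of infusion (Protocol 1.3). These times fall inside the Day 1 to Day 10 diary.

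**3. Which rule governs?** Take a subject with nausea at baseline that worsens some hours after infusion.
- 7.3.2 and 7.6.1: if it is seen as an influenza symptom, not an AE unless the Investigator decides otherwise.
- 9.3.8: an AE if related to study medication.
- 10.1, general text: if it is seen as an influenza symptom, an AE only if it results in an SAE.
- 10.1, footnote a: report it as a worsened AESI.

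The answers differ, and no passage ranks them.

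**4. Can FluPRO supply the missing grade?** For vomiting and diarrhea, SAP 16.3 says: "These questions have possible answers of 0 times, 1 time, 2 times, 3 times, 4 or more times". Protocol Appendix 2 grades diarrhea by loose stools per day: Grade 1 at 3–4, Grade 2 at 5–7, Grade 3 above 7. The top FluPRO answer therefore spans Grades 1 to 3. For vomiting, Grade 2 is 2–5 episodes and Grade 3 is more than 6, so the top answer spans both. The moderate-event rule in 5.6 and the Grade 3 rule in 8.3 could not be rebuilt from the diary.

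**5. Illustration of the effect on 5.6.** Let p be the true proportion of subjects with a GI event and c the share of those subjects recorded in EDC. Neither is given for this trial; both are assumptions. If subjects are independent, the recorded count in n subjects is binomial (n, p × c). The recorded rate is expected to fall below a threshold T once c < T/p.

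For the 50% rule with n = 50 (at least 25 recorded) and p = 60%, break-even capture is 0.50/0.60 = 83%.

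| Capture c | p × c | P(recorded rate ≥ 50%) |
|---|---|---|
| 100% | 60% | 0.94 |
| 90% | 54% | 0.76 |
| 80% | 48% | 0.44 |
| 70% | 42% | 0.16 |
| 50% | 30% | 0.002 |

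For the 25% moderate rule with n = 50 (at least 13 recorded) and p = 35%, the probabilities are 0.93 at full capture, 0.68 at 80% and 0.09 at 50%.

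The 60% is a rate among whichever subjects the rule counts, and 5.6 does not say whether that means each arm or all arms. If both active arms had 60% and placebo none, the pooled rate would be (60 + 60 + 0)/3 = 40%, below 50% even with every event recorded. Prior GI rates range from 6/7 = 85.7% in the first challenge cohort to 2/12 = 16.7% and 1/11 = 9.1% at 2300 mg with the two-drug pretreatments in VIS410-102. The 60% is thus not a forecast.

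**The case against.** The best answer is that the protocol, read as a whole, wants these events reported. The exclusion covers symptoms of influenza, not every FluPRO item. The influenza symptoms named in 9.3.8 and 10.1 include no GI term, and neither does inclusion criterion 5. Section 7.3.2 leaves room for the Investigator's opinion. Section 7.6.1 sends the site to Section 10 for reporting procedures, where footnote a answers the worsening-nausea case directly. Subjects are counseled on GI AEs before discharge, AESIs have their own row in the schedule, and the eCRF has an AESI field. The DSMB also reviews all available safety data and may ask for more meetings, so the rate rules are not its only route to a GI signal.

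Most of this stands, and it favours reporting. It does not close the gap. Both symptom lists open with the word including, so they are not exhaustive. SAP 9.1.1 presents the GI items as influenza symptoms. Neither 7.3.2 nor 7.6.1 exempts AESIs. An exception that rests on opinion or causality will be applied unevenly in a blinded trial. Section 5.6 does not name FluPRO among the DSMB's sources.

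A reader might go further and infer that GI AESIs are barred from the AE record, so that no GI rule could ever be met. The documents do not support that: the bar is conditional, other text requires reporting, and 8.3 counts GI symptoms without naming a data source. Nor do these rules set the dose. Those in 5.6 convene the DSMB, the one in 8.3 pauses dosing, and any downward adjustment is at the DSMB's discretion.

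**Conclusion.** The point holds as an unresolved contradiction among 7.3.2, 7.6.1, 9.3.8 and 10.1. Where a site reads 7.6.1 literally, GI AEs are under-recorded. The AESI proportion in the primary endpoint and the GI rates behind the 5.6 convening rules are then biased downward, with grades that FluPRO cannot recover. Where every site follows 10.1, nothing is lost.

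The size is unknown, because the documents give no capture rate. The illustration shows only that modest under-recording can matter when the true rate is moderately above a threshold: a fall from full to 80% capture takes the chance of reaching the 50% rule from 0.94 to 0.44. It assumes 50 subjects, a true rate of 60%, and independent recording with the same probability for each affected subject. If the true rate is below 50%, the convening rule would not be expected to be met even at full capture, but the primary endpoint proportion is still understated.

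**What to change.** State in 7.3.2 and 7.6.1 that an event on the 10.1 AESI list that starts or worsens after the start of infusion is recorded in EDC as an AE/AESI with a DMID grade, even when the subject also enters it in FluPRO. Align the exceptions in 9.3.8 and 10.1 with that statement and repeat it in the eCRF completion guidance.

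Separately, the sponsor should reconcile GI adverse events in 5.6 with Grade 3 GI symptoms in 8.3 and name the data source for each. Thresholds and dosing rules are the sponsor's to set and are not questioned here.

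The cost is a few sentences of protocol text and site guidance. The downside is small: some GI events caused by influenza will be recorded as AEs, in all arms.
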